# 5.3.4 Treatment

- 1. Subjects will be randomized in a 1:1 ratio to receive study drug (convalescent fresh frozen plasma) versus standard plasma, one unit of FFP, approximately 250 ml. A single dose of CCP will be provided
- 2. Study drug: The investigational product is anti-SARS-CoV-2 convalescent fresh frozen plasma, ABO compatible with the patient. Convalescent plasma for this trial will be obtained from Vitalant (or American Red Cross if necessary.) Donor screening and plasma collection are not conducted as study specific procedures and will be conducted by the collaborating blood bank according to their current SOP. Patients identified as having recovered from COVID-19 will serve as potential donors. Potential donors will be screened using an anti-SARS-CoV-2 serologic assay and antibody levels will be determined. Donors will be screened for standard transfusion-transmitted infections (e.g. HIV, HBV, HCV, West Nile Virus, HTLV-I/II, *T. cruzi*, Zika virus) both with the uniform donor history questionnaire (DHQ) and FDA licensed blood donor screening tests as required by FDA. Plasma will be collected using apheresis technology or via separate from a whole blood donation.
- 3. Control plasma will be obtained from Vitalant (or American Red Cross if necessary) and will be either collected prior to 12/1/2019 or tested and confirmed to be negative for anti-SARS-CoV-2.
- 4. Convalescent plasma will undergo testing to evaluate for anti-SARS-CoV-2 antibodies;
- 5. A sample of the convalescent plasma will be stored for future study to investigate total antibody quantitation, neutralizing antibody activity, and future evaluation of other correlates of immunity and COVID-19 related analyses.
- 6. Both treatment and control plasma will be in standard plasma bags, with International Society of Blood Transfusion (ISBT) labels. The convalescent plasma will be additionally labelled as "COVID 19 Convalescent Plasma" and will have a tie tag indicating "New Drug – Limited by Law to Investigational Use."
- 7. Study investigators analyzing the data and participants will be blinded to the randomization. It may not be feasible to blind nursing staff to the treatment assignment to ensure proper ABO checking of the plasma unit at bedside per standard transfusion procedures, but every effort will be made to preserve blinding of the investigators, participant, and primary team providing care. An unblinded research assistant who is not involved in other aspects of the study will randomize the participant once enrolled. Randomization will be provided to an unblinded provider who is not part of the care team who will place the order for the plasma (CCP vs. control plasma) using a paper order that will not be part of the electronic medical record.

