# 3 PROTOCOL SUMMARY

Long title: A randomized controlled adaptive study comparing COVID-19 convalescent plasma (CCP) to non-immune plasma to limit coronavirus-associated complications in hospitalized patients.

Sample Size: n=50

**Study Population:** Hospitalized COVID-19 patients aged ≥18 years with respiratory symptoms and hypoxia, who do not currently require mechanical ventilation, enrolled within 3 days of admission to the hospital OR within 14 days of initial onset of symptoms.

Study Duration: May 25, 2020 to April 30, 2021

**Study Design**: This randomized, pragmatically blinded, placebo-controlled, adaptive trial will assess the efficacy and safety of anti-SARS-CoV-2 convalescent plasma in hospitalized patients with acute respiratory symptoms up to 14 days after the onset of initial symptoms.

A total of 50 eligible subjects will be randomized in a 1:1 ratio to receive either convalescent fresh frozen plasma from blood donors who have recovered from COVID-19 containing antibodies to SARS-CoV-2 or control (standard fresh frozen plasma collected prior to 12/1/2019 or with documented negative SARS-CoV-2 antibody). Should additional anti-COVID agents (anti-viral and/or anti-inflammatory) become available for use as standard of care during implementation, the sample size will be recalculated and increased to account for the estimated impact that these agents may have on the reducing the progression to the primary endpoint of severe hypoxemia.

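### Participant blinding has no protection at the level of the bag: only the convalescent unit carries an identifying label and tag, and units are checked at the bedside

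*Combined protocol and SAP*

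**What the plan says.** The protocol summary (Section 3) describes the design in these terms: "This randomized, pragmatically blinded, placebo-controlled, adaptive trial will assess the efficacy and safety". Section 5.3.4 (Treatment) supplies the detail.

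- **Packaging common to both arms:** "Both treatment and control plasma will be in standard plasma bags, with International Society of Blood Transfusion (ISBT) labels".
- **Marks on the active arm only:** "The convalescent plasma will be additionally labelled as" COVID-19 convalescent plasma, and the unit "will have a tie tag indicating" investigational use. Nothing equivalent is described for control plasma.
- **Who is blinded:** "Study investigators analyzing the data and participants will be blinded to the randomization". This sentence carries no qualification.
- **Who may not be blinded:** "It may not be feasible to blind nursing staff to the treatment assignment to ensure proper ABO checking of the plasma unit at bedside".
- **What is promised beyond that:** "every effort will be made to preserve blinding of the investigators, participant, and primary team providing care".
- **Concealment steps given:** a research assistant with no other study role randomizes; an unblinded provider from outside the care team orders the plasma; the order is on paper and stays out of the electronic record.

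**The concern.** Two consecutive items of Section 5.3.4 pull against each other. One gives the active unit a label naming the product and a tag, and gives the control unit neither. The next says participants are blinded and has the unit checked at the bedside. A participant, or a member of the primary team present at the time, could learn the arm from the bag.

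This matters because several outcomes depend on judgement:

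- The primary endpoint is mechanical ventilation or death, and the decision to intubate, including its timing, is made by the treating team.
- The 8-point ordinal scale includes oxygen support, discharge status and limitation of activities.
- Symptom screens run to Day 120 and rest on what the participant reports.

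Knowledge of the arm could shift any of these without any effect of the plasma.

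**Working it through.** The plan gives no figure for this point, so the check is a comparison of the provisions on labelling, blinding and administration.

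**Step 1. What distinguishes the arms physically.** Section 5.3.4 gives both arms the same type of bag with standard transfusion labels. The product label and the tie tag are then added to convalescent units only. On the text, every active unit carries a distinguishing mark and no control unit does.

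**Step 2. What each concealment step covers.**

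| Step in Section 5.3.4 | Hides the allocation or order | Hides the bag |
|---|---|---|
| Unblinded research assistant randomizes | Yes | No |
| Provider outside the care team places the order | Yes | No |
| Paper order kept out of the electronic record | Yes | No |
| General promise of every effort | States an aim | No procedure given |

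Sections 3, 4.1.3, 5.3.4, 5.3.6 and the Day 1 procedure describe no cover, over-label or screen, and no dummy label for the control unit.

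**Step 3. Opportunity for exposure.** Participants are not mechanically ventilated at entry (Section 3). The unit is checked at the bedside (Section 5.3.4). Volume is about 250 ml (Section 5.3.4) and the rate is at most 500 mL/hour (Section 5.3.6):

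minimum infusion time = 250 mL ÷ 500 mL/hour = 0.5 hour, or about 30 minutes.

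Vital signs are taken just before the infusion, 10-20 minutes after it starts, at its completion, and 30-60 minutes after it ends (Day 1 procedure). Staff are therefore with the participant while the unit is present.

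**Step 4. Whether the endpoint rules close the gap.** Section 6.2.1 sets ventilator criteria and external adjudication for intubations done for reasons other than hypoxia or hypercarbia. It does not provide for review of the decision to intubate for hypoxia, where knowledge of the arm could act. Death from any cause is not open to the same influence in how it is ascertained.

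**Step 5. How firm each blinding claim is.** The participant claim is unqualified. The primary-team claim is a promise of effort. The order-level steps give the primary team some real protection, because they keep the allocation out of the record that team uses. The gap is therefore larger for participants than for the primary team.

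**The case against.** The best defence is that the plan is candid. It calls the blinding pragmatic, concedes that nurses may be unblinded, and sets up real steps to keep the allocation from the people who decide on intubation. The exposure may be as short as about 30 minutes against a 14-day endpoint. All of that stands. It narrows the point to the bag, but it does not supply a bag-level step or qualify the sentence saying that participants are blinded.

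A reader might infer more than the documents support:

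- **That the trial is in effect open-label, with the arm readable by anyone nearby.** This is an inference. The text does not say the label faces the participant, that the bag hangs uncovered, or that the primary team attends the infusion, and it does not exclude an undocumented cover.
- **That there is no concealment at all, or that the primary team is flatly declared blinded.** Neither is so. The order is concealed, and the primary team is covered only by a promise of effort.
- **That the fragility of the primary test measures the harm.** With 25 per arm, the two-sided Fisher test gives p = 0.049 for 7 against 1 events and p = 0.138 for 7 against 2. Any single changed event, from any cause, would do the same. This describes a trial of 50, not the effect of a label.
- **That false-positive risk is known to be inflated.** Assume no true effect, a 32% event rate in control (the plan's assumption in Section 6.1), and a shift in the active arm only. The chance of a significant apparent benefit is 1.2% with no shift, and 2.4%, 4.8%, 9.0% and 16.3% if the observed active rate falls to 28%, 24%, 20% and 16%. The nominal level in that direction is 2.5%. The smallest of these shifts leaves the risk below nominal and the larger ones do not. The documents give no basis for choosing among them.

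A fair practical objection also stands: a cover put on after a check done in the participant's view would come too late for that participant. The fix has to deal with where the check takes place.

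**Conclusion.** The concern holds in a limited form. Section 5.3.4 marks the convalescent unit alone, has the unit checked at the bedside, states that participants are blinded, and describes nothing that hides the bag. Participant blinding therefore lacks bag-level protection, and primary-team blinding lacks it to a lesser degree. Intubation decisions and the activity and symptom items are exposed to possible bias of unknown size.

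This rests on two assumptions: that the label can be seen in ordinary handling, and that no cover is used beyond what the protocol describes. If a cover is already in use, stating it in the protocol, together with where the check is done, resolves the point. The matter is worth correcting before further enrollment, but it does not invalidate the trial.

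**What to change.** Keep the required label and tag. Add to Section 5.3.4 and to the Day 1 procedure that:

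1. units in both arms receive an identical opaque cover over bag and tag;
2. the identity and ABO check is done out of the view of the participant and primary team, where transfusion procedure allows;
3. the cover stays on until the bag is removed, apart from any lifting needed for inspection.

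If this cannot be done, restate Section 5.3.4 and the summary to say that participants and bedside staff may be unblinded, so that results are read accordingly.

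The cost is a simple supply item and a few lines of text; the documents give no price, so a small cost is an assumption. Two limits remain: the cover must be lifted for inspection, and the nurse stays unblinded and in contact with the participant and team.

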# 5.3.5 **Randomization:**

1. Subjects enrolled in the study will be randomized using a web based randomization procedure to receive convalescent plasma versus non-immune plasma at a 1:1 ratio.

# 5.3.6 Study drug administration

0. Drug will be administered within 24 hours of randomization

- 1. Infusion rate  $\leq$  500 mL/hour
- 2. Pretreatment to minimize transfusion reactions (e.g. acetaminophen, diphenhydramine) may be given at the discretion of the clinical care team.
- 3. If an AE develops during infusion, the infusion may be slowed or stopped as per investigator's decision.
  - Most reactions to plasma are relatively minor and the infusion can generally be continued. Infusion site burning and non-allergic systemic effects can generally be managed with slowing of the infusion. Infusion can generally be continued in cases of itching or hives after pausing the transfusion, administering antihistamines, and observing the patient for worsening.
  - Severe allergic reactions such as, bronchospasm and hypotension, generally require discontinuation of the infusion.

# 5.3.7 **Concomitant medications**

Concomitant medications will be documented on the Case Report Form (CRF) up to day 15.

- Antibiotics
- Anticoagulation
- Any COVID-19 related treatment, including RDV
- Corticosteroids (> 10 mg prednisone equivalent)
- Blood products

After this time, only medications related to COVID-19 treatment will be documented for days 16-120

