#### 4.1.2 Known potential risks

A theoretical risk of administration of convalescent plasma is the phenomenon of antibody-mediated enhancement of infection (ADE). ADE can occur in viral diseases, such as dengue and involves an enhancement of disease in the presence of certain antibodies. For coronaviruses, several mechanisms of ADE have been described, including the theoretical concern that antibodies to one type of coronavirus could enhance infection to another strain [16]. It may be possible to predict the risk of ADE in SARS-CoV-2 experimentally, as proposed for MERS [16]. Since the proposed use of convalescent plasma in the COVID-19 epidemic would rely on preparations with high titers of antibody against the same virus, SARS2-CoV-2, ADE may be unlikely. Available evidence from the use of convalescent plasma in patients with SARS1 and MERS [17] demonstrated it is safe and there were no adverse effects in a pilot study of patients with COVID-19 [14]. Nevertheless, caution and vigilance will be exercised to use clinical and laboratory measures to detect evidence of enhanced infection.

Another theoretical risk is that CCP to those exposed to SARS-CoV-2 may prevent disease but modify the immune response such that those who are treated may mount attenuated immune responses. This may leave them vulnerable to subsequent re-infection. Passive antibody administration before vaccination with respiratory syncytial virus attenuated humoral but not cellular immunity [18]. This will be investigated as part of this clinical trial by comparing immune responses in those who receive standard plasma and convalescent plasma. If responses differ, those with attenuated levels could be vaccinated against COVID-19 when a vaccine becomes available. Nonetheless, these concerns are modest compared to the possible benefit of reducing the risk of respiratory failure and avoiding mechanical ventilation.

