# Day 29: (in person visit if feasible, phone contact if not)

1. COVID-19 symptom screen (fevers, cough, shortness of breath)

2. Assessment of clinical status (8-point ordinal scale) & WHO 11 point scale[27] (added to facilitate data analysis across data sets)

3. Oxygenation status: current FiO2 or liters of O2, route of oxygen, and oxygen saturation or PaO2 (if available)

4. New medical conditions, AE evaluation, concomitant medications (only recorded if treatment given for COVID-19 after day 15)

5. CBC, inflammatory markers (if seen in person)

6. Blood for stored testing, if feasible (3 EDTA, 1 SST)This will include serological testing for SARS CoV-2 antibodies

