# Day 120 In-person (if feasible)

- 1. COVID-19 symptom screen (fevers, cough, shortness of breath)
- 2. Assessment of clinical status (8-point ordinal scale)
- 3. New medical conditions, AE evaluation
- 4. Serological testing: anti-SARS CoV-2 antibody levels

5. Blood for stored testing, if feasible (3 EDTA, 1 SST). This will include serological testing for SARS CoV-2 antibodies

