# 6.2.5 Analysis of the anti-SARS-CoV-2 levels and inflammatory markers.

Analysis of antibody levels will primarily be descriptive, comparing the geometric mean antibody levels at days 1,2,5,8,15, 29, and 120 between the randomized arms. Furthermore, it is of interest to describe the entire distributions of anti-SARS-CoV-2 antibody levels by randomized arms and contrast these distributions. Therefore, we will use quantile regression in order to describe whether there is a shift or change in the titer distribution between randomized arms. Given that repeated measures of antibody levels will be obtained, we will account for the correlation in measures within individuals using a cluster bootstrap

33

in order to properly estimate the p-value and 95% confidence intervals. Similar analysis will also be applied to lymphocyte counts on days 1,2,5,8,15, 29 hematological measurements (D-dimer, ferritin, hsCRP) on days 1,2,5,8,15, 29, 29, and other lab measures showing right-skewed distributions. Exploratory analyses of antibody isotypes, neutralizing antibody activity, antibody affinity, glycosylation and T-cell responses will be conducted to compare between arms and over time.

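### COVID-19 vaccination and non-COVID plasma or immunoglobulin are not recorded after Day 15, which could dilute the exploratory Day 120 antibody comparison

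*Combined protocol and SAP*

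**What the plan says.** Section 5.3.7 opens with a full list that includes blood products: "Concomitant medications will be documented on the Case Report Form (CRF) up to day 15". From then on, "only medications related to COVID-19 treatment will be documented for days 16-120". The Day 29 visit list repeats the limit: "concomitant medications (only recorded if treatment given for COVID-19 after day 15". Table 1 appears to carry the same limit across the late visits. The Day 120 list has serology and "New medical conditions, AE evaluation", but no medication or vaccination item.

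Section 4.1.2 describes a theoretical risk that convalescent plasma attenuates the recipient's own immune response, and makes a commitment: "This will be investigated as part of this clinical trial by comparing immune responses in those who receive standard plasma and convalescent plasma". It adds that, if responses differ, "those with attenuated levels could be vaccinated against COVID-19 when a vaccine becomes available".

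Section 6.2.5 describes a mainly descriptive analysis "comparing the geometric mean antibody levels at days 1,2,5,8,15, 29, and 120 between the randomized arms", with quantile regression and a cluster bootstrap, plus exploratory work on isotypes, neutralizing activity, affinity and T-cell responses. It has no rule for samples taken after vaccination or after a further antibody-containing product. Section 3 gives the study period as "May 25, 2020 to April 30, 2021".

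**The concern.** Section 4.1 says that protection from transferred immunoglobulin can last weeks to months. Early samples in the convalescent arm may therefore mix donor antibody with the patient's own. Day 120 is the scheduled sample furthest from the infusion, so it is the antibody measurement best placed to show attenuation. It also leaves the most time for something else to raise antibody levels.

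Two exposures that could do so are outside the recording rule: COVID-19 vaccination, and plasma or immunoglobulin given for a non-COVID reason. The protocol treats the second as important at entry, since exclusion criterion 4 in Section 5.3.2 bars anyone who received such products in the preceding three months. That control is not carried through follow-up.

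If some patients are vaccinated before their Day 120 sample, vaccine-induced antibody is counted as response to infection. Where uptake and post-vaccine levels are similar in both arms, this pulls the geometric mean ratio towards 1. Without exposure dates in the database, the analysis cannot show how much of the observed ratio is affected.

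**Working it through.** The documents give no effect size, standard deviation or power for the antibody comparison, so there is no planned figure to reproduce. Three checks apply.

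**1. What is recorded after Day 15**

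| Exposure | Captured, days 16-120? | Basis |
|---|---|---|
| Antibody product given as COVID-19 treatment | Yes | 5.3.7; 5.3.8 also asks for later anti-COVID-19 treatment to be recorded |
| Plasma or immunoglobulin for another reason | No | Blood products are listed only to Day 15 |
| COVID-19 vaccine | No | Not a treatment; no item at any visit |

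**2. When Day 120 samples fall**

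Take enrollment as Day 1 and assume that the stated study period includes follow-up.
- Earliest Day 120: 25 May 2020 + 119 days = 21 September 2020.
- Latest enrollment with Day 120 by 30 April 2021: 30 April 2021 − 119 days = 1 January 2021, or 15 January 2021 using the 14-day visit window.

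Day 120 sampling thus runs from about September 2020 to April 2021. The documents say only that no vaccine existed at the time of writing and that one was foreseen. Whether any Day 120 sample followed vaccination is an assumption.

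**3. Size of the dilution**

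Assumptions: a true Day 120 geometric mean ratio (convalescent to control) of 0.50; a share v vaccinated in each arm, unrelated to antibody level; vaccinated patients reach the same level in both arms. On the log scale:

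log(observed ratio) = (1 − v) × log(0.50) + v × log(1), so observed ratio = 0.50^(1 − v).

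| v | Observed ratio |
|---|---|
| 0% | 0.50 |
| 10% | 0.50^0.90 = 0.54 |
| 25% | 0.50^0.75 = 0.59 |
| 50% | 0.50^0.50 = 0.71 |

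The height of the post-vaccine level does not enter the ratio, but it does add spread. If vaccinated patients sit 10-fold above unvaccinated controls, each arm's log10 variance is SD² + v(1 − v)(V − m)². Here V = 1, m = 0 for control and m = log10(0.50) = −0.301 for convalescent plasma. For 25 per arm, SD 0.4 and v = 20%:
- Control variance: 0.16 + 0.16 × 1 = 0.320.
- Convalescent variance: 0.16 + 0.16 × 1.301² = 0.431.
- Standard error: √(0.751 / 25) = 0.173.
- Difference: 0.80 × 0.301 = 0.241.
- Power at two-sided 0.05: Φ(0.241/0.173 − 1.96) = 28%, against 76% with no vaccination.

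With 15 per arm and SD 0.6, the corresponding figures are 14% and 28%. All of these inputs are assumed.

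**The case against.** The strongest reply is that this is a small gap in a secondary matter. Antibody response does not appear in the objectives tables, and its analysis is mainly descriptive. Late blood is drawn only when the patient can attend in person, from at most about 25 per arm. Uptake before Day 120 may have been zero, and then there is no bias from this source. At 10% uptake the ratio moves only from 0.50 to 0.54. Section 9.6.1 makes medical records the source documents, so some vaccination dates might be recovered later. All of this stands, and it limits the weight of the point. It does not remove it: abstraction afterwards may be incomplete, and the plan does not call for it.

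Three stronger readings are tempting, and the documents do not support them.
- *All later antibody products go unseen.* Convalescent plasma or any other product given as COVID-19 treatment falls within Sections 5.3.7 and 5.3.8 and is recorded.
- *Low responders would be vaccinated first, so attenuation would be hidden or reversed.* Under the 10-fold model, uptake of 10% in control and 30% in the convalescent arm would give a ratio of 0.98. But Section 4.1.2 places such vaccination after a difference between arms has been found. Section 5.3.4 blinds participants and aims to blind the care team, and Section 9.5 plans no return of results from stored samples. The documents show no route by which study titres would steer vaccination before Day 120.
- *The trial cannot test attenuation.* Section 4.1.2 does not name Day 120, and the Day 29 antibody, neutralizing and T-cell data also bear on the question.

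**Conclusion.** The recording gap is real. As written, the plan does not capture COVID-19 vaccination at any visit, or non-COVID plasma and immunoglobulin after Day 15, and Section 6.2.5 does not say how samples taken after such exposure are handled. Because the protocol itself promises the immune-response comparison and anticipates a vaccine, this is worth correcting.

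The supported consequence is possible dilution of an exploratory comparison, not its invalidation. On the stated assumptions a true ratio of 0.50 would be observed as 0.50 to 0.71 for equal uptake between 0% and 50%. The documents give no basis for choosing a value within that range. Recording exposure would make the comparison interpretable; it would not make it well powered. The primary endpoint is unaffected.

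**What to change.** - **Recording.** In Section 5.3.7 and the Day 29 and Day 120 visit lists, add the date and type of any COVID-19 vaccine and of any plasma, immunoglobulin or anti-SARS-CoV-2 antibody product received through Day 120.
- **Analysis.** In Section 6.2.5, keep the comparison of all samples by randomized arm. Add a pre-specified sensitivity analysis restricted to samples taken before the first such exposure after the study infusion, and report the number exposed in each arm.
- **Caveat to state.** The restriction selects on a post-randomization event. If exposure is related to antibody level or illness severity, the restricted comparison can itself be biased. It should therefore be read beside the all-sample result and should not replace it.

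The cost is one CRF item at two existing contacts, a short addition to Section 6.2.5, and a smaller sample in the sensitivity analysis. No treatment or visit changes.
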